## 4.4 Schedule of Treatment for each visit

Figure 1 presents the flow diagram of the schedule of treatment for each arm. Table 1 presents the assessments within each arm.

## Staff training

Staff training needs have been identified from our scoping and PPI work and we have developed and tested a 2-hour education and training course in our feasibility study. Training will be provided for staff at each centre in both arms immediately prior to the recruitment period. The educational content follows National Centre for Smoking Cessation and Training (NCSCT) recommendations. This includes: information on smoking prevalence and patterns in the general population and in disadvantaged groups; health effects of smoking and benefits of cessation; evidence based smoking cessation treatment; misperceptions around smoking cessation in the context of other addictions and mental illness and study importance. Additionally, staff in the EC arm will be provided with information on the evidence base of EC use and effectiveness. Information about how to deliver correct advice about EC to participants will be provided along with a practical hands-on demonstration and practice around EC assembly, how to use the device, charge it, refill the tank, replace coils and battery safety is also provided. Staff in the UC arm will receive additional information about how to signpost clients to their local SSS.

## **Control Group**

The control intervention will form usual care. Usual care (UC) here is defined as very brief advice (VBA) about smoking cessation and signposting to the local SSS with information about their local service. Although some homeless centres do offer more than this, this is not standard practice. In line with the current level of provision for smoking cessation in homeless centres, our control arm will include VBA to quit (in the form of an 'NHS choices' leaflet adapted for this population as used in our feasibility study) and signposting to the local SSS, including information about the location and opening hours of the service. Any centres with an established EC 'in house' provision or EC funding stream will be excluded (although this is uncommon). However, support or provision of EC from local SSS will be permitted as this constitutes part of UC. SSS vary widely in terms of services they offer; although all SSS offer NRT and behavioural support, only 11% of local authority funded SSS in England offer EC, whereas others who consider themselves 'e-cigarette friendly' offer support and advice around EC use.

### **Intervention Group**

Delivery of the EC intervention will be as per our feasibility study (14). Centre staff will provide EC arm participants with a tank-style refillable EC starter kit (e.g., the PockeX as used in our feasibility study, a choice of nicotine strength e-liquids (12mg/mL & 18mg/mL) and flavours (tobacco, menthol or fruit) and an EC factsheet (developed for, and used in, our feasibility study). E-liquids (five 10mL bottles per week) will be supplied for four weeks at weekly intervals by centre staff. Participants will be given time to try different flavours and nicotine strengths at baseline and be permitted to switch between flavours in accordance with documented vaping practices (21). EC charging will be available at homeless centres. Participants receiving this intervention will not be discouraged from accessing their local SSS. Although signposting and the provision of local SSS details do not form part of the EC intervention (as above), if participants make enquiries regarding their local SSS (we believe this would be rare) they can be signposted in the usual way as per homeless centre protocol. This information would be recorded as part of the standard health care utilisation questionnaires administered at each follow up point (see economic evaluation section).

#### 4.5 Measures

- Demographic details, smoking history and housing status
- Fagerstrom Test of Cigarette Dependence (FTCD) (17)
- Motivation to Stop Smoking Scale (MTSS; (18))
- Adverse reactions 13 adverse reactions (nervous, headache, sweaty, weak, nausea, pounding heart, throat/mouth irritation, sleep disturbance, dizziness, shortness of breath, cough, wheezy, phlegm production) based on those reported in our feasibility study (5), the Cochrane review of EC (3) and the English TEC study (19), each rated on a 5-point scale from 1 (not at all) to 5 (extremely)
- Positive effects 5 positive effects (hit, pleasant, satisfying, tastes good, helpful for reducing urge to smoke) based on those most commonly reported in our feasibility study (5)
- Risky smoking practices (sharing cigarettes, pickup up discarded cigarettes, asking strangers for cigarettes) each rated on a 4-point scale (not at all, occasionally, regularly, daily)
- Thoughts about EC (perceptions of harm, usefulness for quitting, acceptability)
- EC support (i.e. from staff at centres and others)
- Unintended consequences (of supplying free EC starter kits) including theft, loss, exchanges, breakages, adding other substances.
- Self-reported smoking status
- End-expired carbon monoxide reading: Collected using a calibrated CO monitor. A reading of <8ppm will be used as a cut-off for abstinence

- Use of EC/NRT (including use in the UC arm). Participants who stop using EC/NRT will also be asked their reasons for doing so.
- European Quality of Life-5 Dimensions (EQ5D) questionnaire at baseline and each follow up point.
- Smoking cessation service and health service use at baseline and each follow up point.
- Use of personal and social services
- AUDIT-C
- Diagnoses of mental illness: binary yes/no response

## 4.6 Outcomes

## 4.6.1 Primary Outcome

Sustained CO validated smoking cessation at 24 weeks using the Russell Standard for cessation trials and intention to treat analysis (i.e., no more than 5 cigarettes since 2 weeks post target quit date [TQD] validated by expired CO <8ppm. Participants lost to follow-up are treated as non-abstainers).

## 4.6.2 Secondary Outcomes

Fifty percent smoking reduction from baseline to 24 weeks; 7-day point prevalence quit rates at 4, 12 and 24 weeks; changes in the frequencies of risky smoking practices (e.g., sharing cigarettes, smoking discarded cigarettes) from baseline to 4, 12 and 24 weeks; cost-effectiveness of the intervention; fidelity of intervention implementation; mechanisms of change; contextual influences and sustainability

[figure not shown]
## 4.7 Study product

As per our feasibility study we will continue to use the Aspire PockeX, a second-generation refillable tank device, the device comes with a charger. We also supply e-liquid once per week for the first 4-weeks, participants have a choice of flavours (2 tobacco, 1 menthol, 1 fruit), and rubber bands designed to reduce tank breakages. We will monitor problems and events associated with product use.

## 4.8 Flow Chart of Study Procedures

Figure 1: Flow Diagram

Effects of E-cigarettes (EC) versus Usual Care (UC) for smoking cessation when offered at homeless centres: a cluster Randomised Controlled Trial (cRCT)

## 4.9 Schedule of Assessment

Table 1: Schedule of enrolment, interventions, and assessments.

	STUDY PERIOD					
	Enrolment	Allocation	Po	st-alloca	tion	Close-out
TIMEPOINT**	Baseline	0	4- week	12- week	24- week	t x
ENROLMENT:						
Eligibility screen	Χ					
Informed consent	Χ					
Allocation		Х				
INTERVENTIONS:						
Usual care		Х				
EC		Х				
ASSESSMENTS:						
Sociodemographic characteristics	Χ					
Mental health status	Х					
CO breath sample	X		Х	Х	Х	
Smoking behaviour (incl. risky smoking practices)	Х		Х	Х	Х	
Motivation to Stop Smoking (MTSS)	Х		Х	Χ	Х	
Fagerström Test of Cigarette Dependence (FTCD)	Х		Х	Х	Х	
7-day point prevalence & 50% smoking reduction			Х	Х	Х	
Thoughts about EC	Χ		Х	Х	Х	
Adverse effects	X		Х	Х	Х	
Use of EC & unintended consequences (EC arm)			Х	Χ	Х	
EC positive effects & EC support (EC arm)			Х	Х	X	
Smoking cessation support	X		Х	X	X	
received  Health-care service use	X		Х	X	X	
Health Related Quality of Life	X		Х	X	X	
Substance use	X					
AUDIT-C	X					
Assessment of main effectiveness outcome					Х	
Debrief					Х	Х

## 4.10 End of Study Definition

The study would be completed, and the REC informed after the final attempt to collect 6- month follow-up data from the last randomised participant.

## 4.11 Subject Withdrawal

Participants will be able to withdraw from the study up until the time the results are written up. This will not affect their use of the homeless centre or impact other treatments. Unless withdrawn participants request otherwise, data collected up to the point of their withdrawal will be used in the study analysis. Participants will be withdrawn if they withdraw their consent to participate. We do not foresee any other reasons to withdraw participants.

## 4.12 Data Collection and Follow up for Withdrawn Subjects

Participants who have requested withdrawal will not be followed up at subsequent follow up points unless they wish to be.

## 5 Adverse event/reaction reporting

## **5.1 General Definitions**

## 5.1.1 Adverse Event (AE) and Adverse Reaction (AR)

An AE is any untoward medical occurrence in a participant who has undergone any research procedure including occurrences which are not necessarily caused by or related to that product. An AE can therefore be any unfavourable and unintended sign (including an abnormal laboratory finding), symptom or disease temporarily associated with the use of the study product.

An AR is an AE that may have a causal relationship with the research procedure that the participant has undergone. All AEs judged by either the reporting investigator or the Sponsor as having a reasonable causal relationship to the study treatment qualify as an AR.

## 5.1.2 Serious Adverse Event (SAE) and Serious Adverse Reaction (SAR)

A SAE/SAR fulfils at least one of the following criteria:

- Is fatal results in death
- Is life-threatening
- Requires inpatient hospitalisation or prolongation of existing hospitalisation
- Results in persistent or significant disability/incapacity
- Is a congenital anomaly/birth defect
- Deemed by the PI to be medically significant

## **5.2 Investigators Assessment**

#### 5.2.1 Seriousness

Adverse events/reactions will be assessed for seriousness by the PI or a medically qualified delegated team member according to the definitions given in section 5.1.2.

#### 5.2.2 Relatedness

The PI or delegate will assess whether there is a reasonable possibility that the AE is related to a trial treatment or procedure.

## 5.2.3 Expectedness

The following ARs are deemed potentially related to the study treatment: nausea, throat/mouth irritation, cough, headache, sweaty, weak and sleep disturbance and these will be rated at each follow up point. The PI or delegate will use this list to determine whether the AE is an expected reaction to the trial treatment or procedure.

## 5.2.4 Severity

Expected AR will be rated by study participants at each follow up point. For any receiving a score of 5 (extremely), participants will be asked whether this has stopped them for doing things that they would normally do as an indication of severity. The severity of the event/reaction will be assessed by the PI or delegate according to the following terms and assessments. The intensity of an event should not be confused with the term "serious" which is a regulatory definition based on patient/event outcome criteria.

**Mild**: Some discomfort noted but without disruption of daily life **Moderate**: Discomfort enough to affect/reduce normal activity

Severe: Complete inability to perform daily activities and lead a normal life

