### EC safety

The most recent Public Health England (PHE) evidence review of the literature (7) presents MHRA yellow card notifications of injuries associated with EC use. To date, these are minimal but there are 3 known fatalities, which may be associated with, but not causally related to, EC use.

In the most recent Cochrane review (3), there was imprecision in the findings on safety as measured by reports of AE and SAEs (the confidence intervals were wide). However, comparison analysis revealed no difference in AEs between nicotine and non-nicotine EC use. Incidents associated with SAE and EC use were low. While there is no clear evidence on the harms associated with nicotine EC use, the report concludes that there remains only a small number of studies by which to analyse and within those, follow-up times are less than desirable to measure health and safety outcomes.

In our feasibility study, 21 possible AE were rated, each on a scale of 0 (not at all) to 100 (extreme). The most commonly reported effects were nervousness, headache, sweating, weakness and nausea, each with a mean score below 20. Nausea and headache along with cough and throat/mouth irritation were also the most commonly reported AE in the Cochrane EC review.

Other areas of safety concern have focused on e-liquid content and vapour emissions. While not risk free, it is now well-evidenced that EC are far less hazardous to the user and bystanders than cigarette smoke, with substantially less toxicants and carcinogens detected in exclusive users (4,7,8). A recently published analysis of 40,785 e-liquid containing products ingredient and emission data to the MHRA from November 2016 to October 2017 (9), highlighted some areas for improvement and concern, notably the large range of ingredients and emissions. The MHRA reporting system is unstandardized in terms of reporting requirements, and for quantified emissions, median levels are for the most part below published safe limits for ambient air. However, the authors conclude that, notwithstanding these suggested improvements, EC remain safer than combustible tobacco smoking. As flavours appeal to smokers switching to EC, a balanced approach to reducing absolute risk while not making the products unappealing is required.

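### Sections 4.5, 5.2.3 and 5.2.4 disagree on which reactions are rated and which ratings trigger the activity question, so six of the 13 rated reactions never trigger it, even at the top score

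*Protocol*

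**What the plan says.** Three places in the protocol bear on this.

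- **Section 4.5 (Measures)** lists "13 adverse reactions (nervous, headache, sweaty, weak, nausea, pounding heart, throat/mouth irritation, sleep disturbance, dizziness, shortness of breath, cough, wheezy, phlegm production"). The scale is given later in the same entry, where the items are "each rated on a 5-point scale from 1 (not at all) to 5 (extremely"). Table 1 in section 4.9 schedules adverse effects at baseline and at 4, 12 and 24 weeks, without limiting the row to one arm.
- **Section 5.2.3 (Expectedness)** gives a shorter list as potentially related to treatment: "nausea, throat/mouth irritation, cough, headache, sweaty, weak and sleep disturbance and these will be rated at each follow up point". It then assigns that list a purpose: "The PI or delegate will use this list to determine whether the AE is an expected reaction to the trial treatment or procedure".
- **Section 5.2.4 (Severity)** picks up the word expected and makes the top score the trigger: "Expected AR will be rated by study participants at each follow up point. For any receiving a score of 5 (extremely"). What a top score leads to is a single question on usual activities, which the section puts in these terms: "participants will be asked whether this has stopped them for doing things that they would normally do as an indication of severity". The same section has the principal investigator or a delegate grade each event or reaction as mild, moderate or severe. All three grades are defined by how far the event disturbs daily life or normal activity.

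Section 5.3 adds that expectedness and severity are recorded as separate items for adverse reactions.

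**The concern.** The sections do not describe the same set of reactions. Section 4.5 has 13 items rated. Sections 5.2.3 and 5.2.4, read alone, speak of rating only the expected ones, and there are seven of those. The activity question hangs on the shorter list.

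This matters because the severity grades turn on activity, and the question in section 5.2.4 is the only structured question on activity that the protocol plans for these reactions. If it is programmed as written, the person grading a top-score report of pounding heart, dizziness or shortness of breath will not have an answer that is available for a top-score report of cough or nausea. The protocol gives no reason for the difference. An analysis plan written later cannot supply answers that were never collected, so the matter belongs in the protocol and the case report form.

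**Working it through.** No sample size, power or error rate is involved. The check is a count and a comparison of lists.

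**Step 1. Reproduce the stated count.** Section 4.5 states 13 reactions, and counting the items listed there gives 13.

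**Step 2. Count the expected list.** Section 5.2.3 names 7.

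**Step 3. Compare the lists.**

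| Rated in 4.5 | Expected in 5.2.3 | Activity question at a score of 5, as 5.2.4 is written |
|---|---|---|
| headache | yes | yes |
| sweaty | yes | yes |
| weak | yes | yes |
| nausea | yes | yes |
| throat/mouth irritation | yes | yes |
| sleep disturbance | yes | yes |
| cough | yes | yes |
| nervous | no | no |
| pounding heart | no | no |
| dizziness | no | no |
| shortness of breath | no | no |
| wheezy | no | no |
| phlegm production | no | no |

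All 7 expected items are among the 13, and nothing on the shorter list is absent from the longer one. Items outside: 13 − 7 = 6. Share: 6/13 = 46%.

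**Step 4. What exists for the six items without the question.**

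- A participant rating from 1 to 5 at each scheduled assessment: yes (section 4.5, Table 1).
- A grade by the investigator or delegate: yes. Section 5.2.4 does not limit the grading by expectedness or by score.
- A severity entry on the case report form for an adverse reaction: yes (section 5.3).
- A structured participant answer on whether activity was stopped: no, at any score.

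Only the last is missing.

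**Step 5. Upper bound on the extra burden if the six are added.** With follow-ups at 4, 12 and 24 weeks, the activity question can now arise at most 7 × 3 = 21 times per participant. With all 13 items it could arise at most 13 × 3 = 39 times. The difference, 39 − 21 = 18, is reached only by someone who scores 5 on all six items at all three visits. The protocol does not say how often a score of 5 is expected, so the typical number cannot be calculated. It can only be lower than or equal to that bound.

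**The case against.** The strongest reply is that severity is well covered already. Every one of the 13 items has a participant intensity score, the investigator grades any event or reaction, and section 5.3 records severity separately from expectedness. The activity question is described only as an indication of severity, and the assessor is not confined to it. This stands, and it limits the finding to one missing piece of structured information.

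A second reply is that the word *any* in section 5.2.4 may have been meant to cover every rated reaction. That is possible, and the case report form with its branching is not shown. But the preceding sentence is about expected reactions, so the natural reading is the narrower one, and a programmer working from the text could follow it.

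A reader might also draw four stronger conclusions, which the protocol does not support.

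- *That six reactions, and all scores of 2 to 4, have no severity grade from the participant.* The 1-5 rating is itself a participant-reported measure of intensity for every item.
- *That asking only at a score of 5 is an error.* A score below 5 could meet the definition of moderate, so the choice has a cost. But limiting a follow-up question to the top score is a trade-off against interview length. It contradicts nothing, and the assessor can still grade such a reaction as moderate.
- *That severity will be biased towards mild, or understated in the arm comparison or to the data monitoring committee.* Nothing says that an unasked question defaults to mild. The comparison planned in the synopsis is of the frequency of adverse reactions. Section 5.4 sends serious events and reactions to the committee, and section 5.2.4 itself separates seriousness from intensity.
- *That leaving nervousness off the expected list is a mistake, because it was common in the feasibility study.* The protocol reports there: "The most commonly reported effects were nervousness, headache, sweating, weakness and nausea, each with a mean score below 20", on a scale of 0 to 100. Nervousness is still among the 13 rated items. A short expected list is also the cautious choice for reporting, because a related serious event outside it counts as unexpected and falls under the 24-hour rule in section 5.4.

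**Conclusion.** The point holds as an inconsistency with a small, definite consequence. Sections 4.5, 5.2.3 and 5.2.4 do not agree on which reactions participants rate or which ratings lead to the activity question. As written, 6 of the 13 rated reactions never lead to it, even at the top score, while the grade that the investigator must give depends on activity. Missing severity grades, bias and understated safety reporting are not shown.

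The conclusion rests on two assumptions: that *any* in section 5.2.4 refers back to expected reactions, and that the form is built as the text reads. If the broader meaning was intended and programmed, what remains is a wording fault in sections 5.2.3 and 5.2.4. The correction is worth making in either case, because it costs little and gives the same basis for grading every monitored reaction.

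**What to change.** Reconcile the three sections as follows.

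- **Section 5.2.4:** replace *Expected AR* with *each of the 13 adverse reactions listed in section 4.5*, so that any of them scoring 5 leads to the activity question. Leave the trigger score as it is.
- **Section 5.2.3:** keep the seven-item list for deciding expectedness only. Remove the clause about rating, or replace it with a reference to section 4.5.
- **REDCap and the case report form:** apply the same branching to all 13 items at each follow-up.

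The cost is a change of wording, a change of branching on an existing questionnaire, and slightly longer interviews for participants who give a score of 5 to one of the six added items.

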## 5.3 Notification and reporting Adverse Events or Reactions

Data on AEs, ARs, SAEs and SARs and will be collected and recorded on the CRF/REDCap including i) whether an AE has occurred; ii) what they event was; iii) whether the AE was deemed serious (i.e. a SAE); iv) whether the AE was deemed related to the trial treatment/procedure (i.e. an AR); v) whether the AR was expected; and vi) severity of the AR. If the AR is **not** defined as SERIOUS, the AR will be recorded in the CRF and the participant will be followed up by the research team.

## 5.4 Notification and Reporting of Serious Adverse Events/Reactions

All SAEs including SARs will be recorded in the participant's notes and CRF. This should include a description of the event, the date and time that the event began and ended (or ongoing), the severity of the event and any action taken in response to the event. SAEs and SARs should be reported immediately to the PI and/or TM. The PI or TM must report **related and unexpected SAEs to the REC/sponsor** via the relevant project page on Haplo (Research and Enterprise Management) within 24 hours of the PI, TM or co-investigators becoming aware of the event. Nominated co-investigators can be authorised to complete SAE forms on Haplo in the absence of the PI/TM at the co-ordinating site. The original hard copy and any subsequent follow up of SAE forms must be kept with the participant CRF under double-lock conditions at the study site until the end of the trial.

SAEs and SARs will also be reported to the DMC and to the funder (NIHR) via uploading DMC minutes and through progress report tasks.

